**Research Application:**

**A. Type of Study: Human**

**B. Brief Summary of Proposal:**

**(1) Project Background:** Mesothelioma is a rare, aggressive and treatment-resistant disease and, in the United States, is caused almost exclusively by exposure to asbestos fibers. Although predominantly associated with the pleura of the lung and peritoneum, mesothelioma may also develop in a variety of other locations in which mesothelial tissue exists including pericardium and tunica vaginalis testis. There is often a lengthy latency period of 40-50 years between exposure and disease onset. The median age of diagnosis is 65 years while the median survival time after diagnosis without treatment is 9 months. Symptoms, where present, may be non-specific, which further contributes to delayed diagnosis. Because patients with mesothelioma may be asymptomatic until very late in the course of their disease, they may have very limited therapeutic options available because advanced disease is less amenable to treatment. With interventions, survival is extended only to 12 months. As a result, patient prognosis is poor, and mesothelioma carries with it a high mortality rate. Further compounding this issue is the fact that the incidence of mesothelioma is low (approximately 2 per 100,000 capita) in comparison with other types of cancer and as a result, little research has been conducted on either the early identification or early treatment of disease. The ability to identify the presence of disease at an early stage or increase clinical suspicion for the presence of disease among asbestos exposed individuals, would enable earlier detection and earlier treatment, thus reducing morbidity and mortality. In this study, the volatile organic compound (VOC) profile from subjects with histologically confirmed mesothelioma will be compared against case-matched control subjects with bilateral pleural plaques or bilateral pleural thickening. Putative markers will then be tested against a blinded cohort to test predictive value of the markers.

**(2) Project Rationale:** This study seeks to identify markers for mesothelioma using a non-invasive technique which samples volatile organic compounds (VOC) in the breath of test subjects (Owlstone Medical Ltd, Cambridge, England). A comparison will be made with an FDA-approved, serum-based assay (Lumipulse Mesomark, Fujirebio Diagnostics Inc., Malvern, PA). Identifying patients who are either predisposed to developing mesothelioma by pleural findings as an indication of asbestos exposure or who may be at an early disease stage, is expected to improve prognosis by limiting disease progression through more effective medical and surgical therapeutics.

**(3) Purpose of Study and/or Hypothesis:** Individuals with pleural mesothelioma are anticipated to have a different volatile organic compound (VOC) profile in comparison with appropriately matched controls. These specific compounds may have a diagnostic potential which enables the early detection of patients with disease before overt clinical symptoms become manifest. Following the identification of putative

biomarkers, the predictive capability of these markers alone and in concert with a serum-based assay, will be tested.

**(4) Anticipated Outcome:** We anticipate that one or more VOC markers in breath samples from affected subjects will be identified using the Owlstone Breath Biopsy sampling methodology which will show an association with the presence of pleural mesothelioma in patients. Furthermore, we will evaluate participant's Lumipulse Mesomark serum assay, comparing those results with the VOC profile to discern parameters of efficacy.

**(5) Importance/Relevance:** Identifying patients who are either likely to develop mesothelioma or who are at an early disease stage, is expected to improve prognosis by limiting disease progression through more effective medical and surgical therapeutics.

**C. References and Supporting Data:** See accompanying Owlstone's Breath Biopsy® The Complete Guide Second Edition as part of this IRB submission and the two 2004 American Radiology Letters to the Editor consisting of a response to a peer-reviewed article on chest radiograph B-readers and the author's reply.

**D. Detailed Plan of Proposed Research:** As submitted in the IRB A-1 Research Application document.

**E. Specific Objectives or Aims:** Specific Aim 1: Identify putative VOC biomarkers in the breath samples of subjects with mesothelioma in comparison with case-matched controls.

Specific Aim 2: Test the predictive capability of VOC biomarkers and serum-based mesothelioma biomarkers both individually and collectively.

**F. Experimental Design:** This will be a prospective, non-randomized, case-controlled study. In Specific Aim 1, the disease status of the study population will not be blinded to the investigators in order to select disease-specific biomarkers. In Specific Aim 2, the Investigators and the analytics team will be blinded to the presence of disease to determine the predictive value of the markers. Predictive capability will be defined by determining the sensitivity, specificity and positive and negative predictive capability of the selected VOC biomarkers in identifying subjects with mesothelioma. In addition, study subjects will also be tested with an FDA approved, serum-based ELISA assay (Lumipulse, Mesomark, Fujirebio). The predictive capabilities of both tests will be evaluated both individually and collectively.

Phase 1 - Discovery of VOCs associated with the presence of mesothelioma: A total of 200 volunteers - 100 with objective evidence of exposure to asbestos and no evidence of mesothelioma, and 100 with histologically confirmed evidence of mesothelioma - will be recruited into this phase of the study with an expected study duration of up to 24 months. Objective evidence of asbestos exposure for purposes of this study include, but may not be limited to, a history of exposure to asbestos and bilateral pleural plaques or bilateral pleural thickening. Radiographic evidence of exposure will be rendered by an A reading, B reading, or an interpretation of a radiologist board certified by the American College of Radiology.

Phase 2 - Validation study to assess the predictive capability, sensitivity and specificity of selected VOCs in identifying subjects with mesothelioma: A total of 100 volunteers - 65 with objective evidence of

asbestos exposure and no evidence of mesothelioma, and 35 with objective evidence of mesothelioma - will be recruited into this phase of the study with an expected duration of up to 12 months. The investigators and testing laboratories will be blinded as to the presence of mesothelioma among the participants.

Phase 2 is contingent on the successful identification of VOCs during the Phase 1 discovery study. If no putative biomarkers are identified in Phase 1 of this study or if the predictive capability proves to be too low, the study will be discontinued.

The following inclusion and exclusion criteria will apply to both Specific Aim 1 and 2 of this study.

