#### **Inclusion Criteria**

- Male or Female subjects over the age of 18
- Reported prior exposure to asbestos
- Radiologically confirmed bilateral pleural plaques or bilateral pleural thickening, or histologically confirmed mesothelioma

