### **Disease type and severity stratification**

- Presence of mesothelioma
- Disease stage classification (IMIG)
- Date of initial mesothelioma diagnosis
- Histologic data
- Radiographic data
- Nature of exposure Acute/chronic exposure
- Presence of benign disease indicators (asbestosis, pleural plaques, thickening of the pleura)

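### No planned estimate addresses the early-detection purpose: IMIG stage is recorded, but sensitivity is defined only for mesothelioma as a single class

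*Combined protocol and SAP*

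**What the plan says.** **Purpose.** B(3) describes the potential use of the markers as one that "enables the early detection of patients with disease before overt clinical symptoms become manifest". B(1), B(2) and B(5) give early-stage identification as the reason the work matters. B(1) adds that "patients with mesothelioma may be asymptomatic until very late in the course of their disease".

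**Cases.** The Inclusion Criteria ask for "Radiologically confirmed bilateral pleural plaques or bilateral pleural thickening, or histologically confirmed mesothelioma". They contain no stage or symptom condition. Section F applies them throughout: "The following inclusion and exclusion criteria will apply to both Specific Aim 1 and 2 of this study". Phase 1 recruits "100 with histologically confirmed evidence of mesothelioma" and Phase 2 recruits 35 cases. Neither phase has an early-stage quota.

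**Accuracy measure.** Section F defines predictive capability as "sensitivity, specificity and positive and negative predictive capability of the selected VOC biomarkers in identifying subjects with mesothelioma". Sections G and H(3) assign the analyses to the two laboratories and add no estimate by stage.

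**Data items.** The list headed Disease type and severity stratification includes "Disease stage classification (IMIG"), together with histology and the date of diagnosis. No strata, analysis or reporting rule follows. Symptom status appears in none of the data lists.

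**The concern.** The use that motivates the study is finding disease before it declares itself clinically. The only sensitivity the plan defines is measured in people whose disease has already been found, with all stages counted together. That figure is an average over whatever stages happen to be recruited, so it can look good while sensitivity in early disease is poor.

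At stake is what the trial may conclude. If Phase 2 ends with a good overall sensitivity and no prespecified figure by stage, the text of section B invites the reader to take it as evidence for early detection. Blinding in Phase 2 guards against biased reading of the samples. It does not change which cases are in the denominator. A stage breakdown produced only after unblinding would be open to selective reporting.

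**Working it through.** **The plan's own figures.** The documents give no alpha, power, target sensitivity, precision or stage distribution behind the sample sizes, so there is no derived figure to reproduce. The counts agree: 100 + 100 = 200 in Phase 1, 65 + 35 = 100 in Phase 2, and 200 + 100 = 300, which matches the 300 subjects in H(1).

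**Inputs.** From section F: 35 Phase 2 cases. Assumed, because the documents are silent: an early share of about 10% to 50% (4, 7, 10 or 18 of 35), late-stage sensitivity of 90%, and early-stage sensitivity of 30%, 50% or 80%. Early means IMIG I–II and late means III–IV.

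**Step 1: what the pooled figure averages.** Pooled sensitivity = (n_early × S_early + n_late × S_late) / 35. With 7 early and 28 late cases:

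- S_early 30%: (7 × 0.30 + 28 × 0.90) / 35 = 27.3 / 35 = 78%
- S_early 50%: (7 × 0.50 + 28 × 0.90) / 35 = 28.7 / 35 = 82%
- S_early 80%: (7 × 0.80 + 28 × 0.90) / 35 = 30.8 / 35 = 88%

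Over the assumed range of early shares:

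| Early cases of 35 | S_early 30% | S_early 50% | S_early 80% |
|---|---|---|---|
| 4 | 83.1% | 85.4% | 88.9% |
| 7 | 78.0% | 82.0% | 88.0% |
| 10 | 72.9% | 78.6% | 87.1% |
| 18 | 59.1% | 69.4% | 84.9% |

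If late-stage sensitivity is set to 80% instead, the row for 7 early cases becomes (2.1 + 22.4) / 35 = 70%, (3.5 + 22.4) / 35 = 74% and (5.6 + 22.4) / 35 = 80%.

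**Step 2: can 35 cases tell these apart?** The exact (Clopper-Pearson) 95% CI for 28/35 = 80% is 63.1–91.6%. It contains every value above except 59.1%, which needs both a roughly half-early mix and 30% early-stage sensitivity. In the other scenarios, a pooled result near 80% does not separate poor from good early-stage sensitivity.

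**Step 3: how precise would a stage I–II estimate be?** Exact 95% CIs for possible results:

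- 3/4: 19.4–99.4%
- 6/7: 42.1–99.6%
- 8/10: 44.4–97.5%
- 14/18: 52.4–93.6%
- 5/9 (an assumed early share of 25%, since 35 × 0.25 = 8.75): 21.2–86.3%

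**Step 4: cases needed for a usable early-stage estimate.** n = 1.96² × S(1 − S) / h². At S = 0.80, h = 0.10 gives 3.84 × 0.16 / 0.01, or about 62 early cases, and h = 0.15 gives about 28. At an assumed 20% early share, that is 310 or 140 cases in total (62 / 0.20 and 28 / 0.20), against the 35 planned.

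**The case against.** The formal aims in section E do not mention stage or symptoms. Aim 1 looks for markers in cases against controls and Aim 2 tests how well they predict. B(3) words early detection as a potential, B(4) anticipates only an association with the disease being present, and B(5) is a statement of relevance. Studying confirmed cases first is a reasonable order of work. All of this stands, and it means the plan does not promise early-stage accuracy. It does not make the pooled figure informative about the use that section B gives as the reason for the study.

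Three stronger readings are tempting, and the documents do not support them.

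- A reader might infer that the result will mainly describe advanced disease. B(1) makes that plausible, but it says only that patients may be asymptomatic until late, and no stage distribution is given. The exclusion of anyone treated for a malignancy in the past 6 months also shifts the case mix, in an unknown direction.
- A reader might infer that the plan commits to pooling, or that Phase 2 could never show a stage effect. Pooling is inferred from silence. Stage is recorded in both phases under a heading that names stratification, so a breakdown is unspecified rather than ruled out. Section D also refers to an IRB application document for the detailed plan. Even so, F, G and H(3) are where such an analysis would be expected.
- A reader might infer that the selected markers will track tumour bulk. Nothing in the documents shows this.

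The assumed sensitivities also have no source. If early-stage sensitivity were 80%, pooling would hide little. The arithmetic shows what could go unseen, not what is likely.

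**Conclusion.** The point holds in a limited form. All cases are already diagnosed, no stage limit or quota exists, and the one defined sensitivity is for "positive and negative predictive capability of the selected VOC biomarkers in identifying subjects with mesothelioma" taken as a single class. Recorded stage enters no stated analysis, and symptom status is not listed. The pooled sensitivity from 35 diagnosed cases therefore cannot by itself support early or pre-symptomatic detection. That conclusion rests on the text alone and does not depend on the stage mix.

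The size of any masking does depend on assumptions. With 7 early cases of 35 and 90% late-stage sensitivity, a range of 30% to 80% in early-stage sensitivity moves the pooled figure only from 78% to 88%, within the 63–92% interval for 28/35. This is a change the sponsor should make because it alters what the trial can conclude at little cost. It does not invalidate Aims 1 and 2 as written.

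**What to change.** In sections F, G and H(3):

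1. Prespecify that Phase 2 sensitivity of the VOC markers, the serum assay and the two combined is reported separately for IMIG I–II and III–IV, with exact 95% CIs, beside the pooled value.
2. Report Phase 1 marker effects by stage descriptively. Do not use stage as a selection rule. With 25 early cases (an assumed 25% of 100) and 100 controls, a standardised difference has a 95% half-width of about 1.96 × √(1/25 + 1/100) = 0.44, so such a rule could discard real markers by chance.
3. Record symptom status (one form item) and the date of the existing staging relative to breath sampling. Do not require restaging, which could add procedures.
4. State that the pooled result supports only detection of established, diagnosed mesothelioma, and that any early-detection statement must rest on the stage I–II estimate and its interval.

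The cost is protocol wording and minor form changes, with no added participants or procedures. The downside is an imprecise early-stage estimate (5/9, for example, has a CI of 21–86%) and a more modest headline claim. The change limits the claim; without many more early cases it will not establish early detection.

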### **Potential Test confounders**

- When did you last smoke
- When did you last drink and what was it
- When did you last eat and what was it
- Time since brushing teeth, or rinsing with anything other than distilled water
- Nebulized inhaled medication less than 2 hours prior to breath collection

**G. Data Analysis:** Phase 1, which is designed to identify putative VOC markers, will be non-randomized and non-blinded. Statistical analysis will be performed by both the Owlstone and Fujirebio laboratories using their trained biostatisticians. Selected biomarkers will then be used in Phase 2. Study subjects in Phase 2 will be anonymized and the Owlstone and Fujirebio laboratory staff will be blinded with regards to disease presence.

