### **H. Materials and Methods:**

(1) Breath sampling masks, collection tubes and the collection apparatus will be provided by Owlstone Medical Ltd (OML) (\$300/breath sampling kit for 300 subjects). OML has developed a breath sampling system for the collection of human breath samples that is comprised of two main parts:

1. ReCIVA® Breath Sampler: the breath sample collection unit, and
2. CASPER: the air supply unit.

The intended use of ReCIVA is to collect samples of Volatile Organic Compounds (VOCs) present in exhaled breath for subsequent laboratory analysis. CASPER is used to provide a filtered ambient air supply to the ReCIVA breath sampler.

The Insulators Union considers that use of the OML breath sampling system as part of the study constitutes use of a diagnostic test system in the laboratory research phase of development. The Insulators Union also considers that the OML breath sampling test system meets the requirements for exemption of diagnostic devices from part 812 IDE regulations as set out in part 812.2(c)(3). The OML devices will therefore be deployed as "Research Use Only" (RUO) products for the purposes of the study. A detailed description of the OML breath sampling system, including a risk assessment, can be found in reference OW-019034-RE attached as part of this IRB submission package.

(2) The serum-based assays will be provided free of charge by Fujirebio.

(3) Statistical Analysis: Descriptive statistics from the study population and statistics intended to determine the predictive capability, sensitivity and specificity of the Owlstone Breath Biopsy, will be conducted by Owlstone biostatisticians. Predictive capability, sensitivity and specificity of the Fujirebio Lumipulse Mesomark assay will be conducted by the Fujirebio biostatisticians.

[figure not shown]

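### Phase 2 is a validation study without a locked classification rule: nothing fixes cut-offs, weights or per-subject calls before disease status is released to those computing accuracy

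*Combined protocol and SAP*

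**What the plan says.** Section F (Experimental Design) describes Phase 2 as a validation study in 35 people with mesothelioma and 65 asbestos-exposed controls. On blinding, it says that "the Investigators and the analytics team will be blinded to the presence of disease to determine the predictive value of the markers" and, in the Phase 2 paragraph, "The investigators and testing laboratories will be blinded as to the presence of mesothelioma among the participants". Section G (Data Analysis) adds: "Study subjects in Phase 2 will be anonymized and the Owlstone and Fujirebio laboratory staff will be blinded with regards to disease presence".

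On who does the analysis, section G states: "Statistical analysis will be performed by both the Owlstone and Fujirebio laboratories using their trained biostatisticians". Section H(3) gives the breath vendor the descriptive statistics and says that "predictive capability, sensitivity and specificity of the Owlstone Breath Biopsy, will be conducted by Owlstone biostatisticians". It gives the corresponding accuracy work for the serum assay to the serum vendor's biostatisticians.

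On what passes from Phase 1 to Phase 2, section G has one sentence: "Selected biomarkers will then be used in Phase 2". Section F requires sensitivity, specificity and positive and negative predictive capability, and asks for the breath and serum tests to be evaluated separately and together.

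The documents state no cut-off, marker weighting, combination rule, holder of the disease key or time of unblinding.

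**The concern.** Phase 2 exists to test, on fresh subjects, markers that were selected with disease status known. That test is unbiased only if the whole rule turning measurements into a positive or negative call is settled beforehand. A list of compounds is not such a rule. It leaves open the threshold, the weights if several compounds are used, and how a breath result is combined with a serum result.

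Blinding the laboratory protects the measurements. It does not protect the classification if the threshold is chosen once disease status is known. The analysts could follow every sentence of the plan and still choose the cut-off that best separates the 35 cases from the 65 controls. Phase 2 would then work partly as a second discovery set, and its reported accuracy would be too high. These 100 subjects are the only validation set in the plan, so the loss could not be repaired after the key is released.

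**Working it through.** **Step 1: who is blinded, and who needs the key.**

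| Task or group | Section | Disease status |
|---|---|---|
| Investigators and analytics team, Aim 2 | F | Blinded |
| Testing laboratories, Phase 2 | F | Blinded |
| Laboratory staff of both vendors, Phase 2 | G | Blinded |
| Statistical analysis, by the laboratories' own biostatisticians | G | Needed for accuracy |
| Sensitivity and specificity of each test, by that vendor's biostatisticians | H(3) | Needed |

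Sensitivity is the number of positive calls among cases divided by the number of cases. Specificity is the number of negative calls among controls divided by the number of controls. Both denominators need disease status, so the key must reach these analysts at some point. Both numerators need a rule for a positive call, and no such rule is handed over.

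**Step 2: what an unlocked cut-off can do.** The plan has no target accuracy or sample-size calculation to reproduce. Only its counts can be checked: 100 + 100 = 200 in Phase 1, 35 + 65 = 100 in Phase 2, and 300 in all, matching the 300 breath kits in section H(1).

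The effect was therefore simulated, with 10,000 runs per AUC.

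- From the plan: 35 cases and 65 controls in Phase 2; 100 and 100 in Phase 1.
- Assumed: one marker of known direction, normal with unit variance in both groups. Its mean is 0 in controls and d = √2 × Φ⁻¹(AUC) in cases; for example, AUC 0.80 gives d = 1.414 × 0.842 = 1.19.
- Assumed: the cut-off c maximises the Youden index, J = sensitivity + specificity − 1.
- True J of a cut-off c: [1 − Φ(c − d)] + Φ(c) − 1.

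| Assumed AUC | Apparent J, cut-off chosen on Phase 2 | True J of that cut-off | Overstatement | Apparent J, cut-off locked from Phase 1 | True J of locked cut-off |
|---|---|---|---|---|---|
| 0.60 | 0.235 | 0.123 | 0.11 | 0.128 | 0.128 |
| 0.70 | 0.366 | 0.267 | 0.10 | 0.273 | 0.275 |
| 0.80 | 0.513 | 0.428 | 0.09 | 0.434 | 0.435 |
| 0.90 | 0.687 | 0.616 | 0.07 | 0.623 | 0.624 |

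The overstatement is in sensitivity plus specificity together. Over AUC 0.70 to 0.90 it averages about 0.05 (0.10 / 2) down to 0.035 (0.07 / 2) for each. A cut-off locked from Phase 1 removes the bias to within simulation error.

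These figures cover one cut-off on one marker. Re-weighting several markers, or choosing a combination rule on the same data, would be further sources of optimism. They cannot be sized without the number of markers, which the plan does not give.

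**The case against.** Several stronger readings are tempting, and the documents do not support them.

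- **The plan contradicts itself.** A reader might infer that blinding the analysts and having them compute accuracy cannot both be done. They can, in sequence: calls are made blind, then the key is released and accuracy is computed. What is missing is the sequence.
- **The blinded analytics team is the vendors' biostatisticians.** This is a reasonable inference, because section G places the biostatisticians within the laboratories and no other analysts are named. But the term is undefined, no section says who makes the calls, and section G's Phase 2 sentence blinds laboratory staff. If separate unblinded statisticians exist, the missing lock remains.
- **The clinical fields will break the blind.** The disease type and severity list includes "Date of initial mesothelioma diagnosis", which would identify cases. Nothing says these fields go to a laboratory before calls are made, and Phase 2 subjects are to be anonymized. The descriptive statistics in H(3) are not tied to a phase or time and could follow unblinding.
- **The serum vendor will tune its assay.** The assay is described as FDA-approved and may have an established cut-off, although none is stated. The exposure lies mainly with the VOC and combined tests.
- **Noise could pass as a validated marker.** In the same simulation a useless marker (AUC 0.50) shows an apparent J of 0.12. But Phase 2 proceeds only if Phase 1 identifies markers, so a pure-noise case is unlikely, even though that gate has no numerical threshold.

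Two further objections limit the point without removing it. Section D refers to an IRB A-1 document for the detailed plan. It may be this same text or a fuller one, and a lock stated there would answer the point. Also, the bias is modest beside sampling error: with 35 cases and sensitivity near 0.72, the 95% half-width is 1.96 × √(0.72 × 0.28 / 35) = 0.15. That half-width describes chance error in either direction, whereas tuning shifts the average upward and an ordinary confidence interval does not account for it.

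**Conclusion.** The concern holds as a missing lock and a missing unblinding sequence. The documents do not say that cut-offs will be set on Phase 2 data. They leave it permitted, because only marker identities are carried forward and nothing requires calls to be fixed before disease status is released.

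If the cut-off were chosen on the Phase 2 data, sensitivity plus specificity would be overstated by about 0.10 at AUC 0.70, 0.09 at 0.80 and 0.07 at 0.90. These sizes rest on one normally distributed marker, equal variances and selection by the Youden index, none of which the plan specifies. The direction of the bias is not in doubt; its size is illustrative. It should be settled before Phase 2 begins.

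**What to change.** In section G, replace the sentence "Selected biomarkers will then be used in Phase 2" with the text below, and make H(3) subject to it:

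> Before Phase 2 begins, the VOC panel, its weighting and cut-off, the serum cut-off (the assay's established cut-off if it has one) and the rule combining the two tests are fixed in a dated document. In Phase 2 each laboratory, including its biostatisticians, receives coded samples without disease status or the disease type and severity fields, and deposits a dated positive or negative call for each subject. The combined call is derived from the fixed rule. Disease status is released only after all calls are deposited, by existing study staff who are not involved in making the calls. Accuracy is computed from the deposited calls. Any rule revised after release is labelled exploratory.

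In section F, state that the analytics team is blinded until the calls are deposited, and say whether that team includes the vendors' biostatisticians.

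The cost is protocol wording, one dated rule document, one dated file of calls per laboratory, and naming existing staff to hold the key. No extra subjects or procedures are needed. The downside is that reported accuracy may look slightly less favourable, because the rule cannot be re-tuned on the validation data.

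### PPV and NPV are planned in a Phase 2 sample recruited at 35 cases to 65 controls with no target prevalence stated, so for an imperfect test the raw values describe only a 35% case mix

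*Combined protocol and SAP*

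**What the plan says.** Section F (Experimental Design) describes the design: "This will be a prospective, non-randomized, case-controlled study". For Aim 2 it then says: "Predictive capability will be defined by determining the sensitivity, specificity and positive and negative predictive capability of the selected VOC biomarkers". The serum assay is brought in alongside: "The predictive capabilities of both tests will be evaluated both individually and collectively".

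The Phase 2 paragraph of Section F fixes the sample at 100 volunteers, 65 of them asbestos-exposed without mesothelioma and "35 with objective evidence of mesothelioma".

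Section B(1) gives the purpose of this phase: "Putative markers will then be tested against a blinded cohort to test predictive value of the markers". It also describes the hoped-for benefit, which is to identify disease early or to "increase clinical suspicion for the presence of disease among asbestos exposed individuals".

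On analysis, Section H(3) assigns to the breath-test company's biostatisticians the "statistics intended to determine the predictive capability, sensitivity and specificity of the Owlstone Breath Biopsy", and gives the assay company the matching task for Mesomark. Sections G and H(3) say who analyses and who is blinded. They give no target prevalence, no re-weighting and no limit on how PPV and NPV are to be read. For the detailed plan, Section D says only: "As submitted in the IRB A-1 Research Application document". If that is a separate document, it was not supplied.

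**The concern.** PPV and NPV depend on how common the disease is among the people tested. In a cohort sampled from the target population, the data carry that information. In a case-control sample they do not, because the investigators choose the number of cases. Here 35 in 100 is a quota and estimates nothing about asbestos-exposed people.

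Predictive value is a stated purpose of Phase 2, and the motivation is earlier detection among exposed people. A reader of the results could therefore take a raw PPV as the chance that an exposed person with a positive breath test has mesothelioma. If disease is much rarer than 35% in that population, the raw PPV is far too high and the raw NPV too low. The same would apply to Mesomark and to the combined test if PPV and NPV are reported for them. Section F's definition names only the VOC markers, but evaluating both tests individually and collectively makes that the natural reading.

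**Working it through.** **Inputs from the documents.** Phase 2 has 35 cases and 65 controls (Section F). 35 + 65 = 100 agrees with the stated total, and the case share is 35/100 = 35%. The plan gives no expected accuracy or precision target, so it has no figure of its own for PPV or NPV to reproduce. The only frequency is a background incidence of about 2 per 100,000 in Section B(1). That is not a prevalence and is not specific to exposed people, so it is not used here.

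**Assumptions.** All sensitivities (Se), specificities (Sp), prevalences (p) other than 35%, and test-result counts below are illustrative.

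**Formulas.**

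- PPV = Se·p / [Se·p + (1 − Sp)(1 − p)]
- NPV = Sp(1 − p) / [Sp(1 − p) + (1 − Se)p]

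**Step 1: one test, several prevalences (Se 80%, Sp 85%).** At p = 35%, PPV = 0.80 × 0.35 / (0.80 × 0.35 + 0.15 × 0.65) = 0.280 / 0.3775 = 74.2%. At p = 1%, PPV = 0.0080 / (0.0080 + 0.1485) = 5.1%.

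| Prevalence | PPV | NPV |
|---|---|---|
| 35% (study mix) | 74.2% | 88.8% |
| 10% | 37.2% | 97.5% |
| 5% | 21.9% | 98.8% |
| 1% | 5.1% | 99.8% |
| 0.1% | 0.5% | 99.98% |

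**Step 2: other accuracies.**

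| Se / Sp | PPV at 35% | PPV at 5% | PPV at 1% |
|---|---|---|---|
| 70 / 80 | 65% | 16% | 3.4% |
| 90 / 95 | 91% | 49% | 15% |
| 95 / 99 | 98% | 83% | 49% |

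The gap narrows for a very specific test but remains. Raw PPV stops depending on prevalence only if specificity is exactly 100%, and raw NPV only if sensitivity is exactly 100%.

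**Step 3: an uninformative test.** With Se = Sp = 50%, the sample returns PPV 35% and NPV 65%. Those figures come from the quota alone.

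**Step 4: with sampling error, at Phase 2 size.** Suppose 28 of 35 cases test positive and 55 of 65 controls test negative (7 false negatives, 10 false positives).

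- Se = 28/35 = 80.0% (exact 95% CI 63.1–91.6%). Sp = 55/65 = 84.6% (73.5–92.4%).
- Raw PPV = 28/38 = 73.7% (56.9–86.6%). Raw NPV = 55/62 = 88.7% (78.1–95.3%).
- LR+ = (28/35)/(10/65) = 5.20 (log-method 95% CI 2.87–9.42). LR− = (7/35)/(55/65) = 0.236 (0.121–0.462).
- With odds = p/(1 − p), projected PPV = odds·LR+ / (1 + odds·LR+) and projected NPV = 1 / (1 + odds·LR−).

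| Assumed prevalence | Projected PPV (95% CI) | Projected NPV (95% CI) |
|---|---|---|
| 5% | 21.5% (13.1–33.1%) | 98.8% (97.6–99.4%) |
| 1% | 5.0% (2.8–8.7%) | 99.8% (99.5–99.9%) |
| 0.1% | 0.5% (0.3–0.9%) | 99.98% (99.95–99.99%) |

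None of these projected intervals overlaps the raw interval for the same measure. They reflect sampling error in Se and Sp only.

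**The case against.** The strongest reply is that the plan does not commit to the misreading. Section F gives no formula for PPV or NPV, and nowhere do the documents say that Phase 2 values will be applied to exposed people at large. The sentence on clinical suspicion in Section B(1) is motivation. Section H(1) presents the breath system as research use only, so no patient-level decision is shown to rest on the Phase 2 PPV. The detailed plan may also sit in a document that was not supplied. All of this stands, and it limits the point to the supplied text and to how PPV and NPV are read outside the sample. It does not remove the point. Section F itself sets the definition, predictive value is a stated purpose, and following the text as written yields figures tied to a quota.

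A second reply is that projections can mislead too. This also stands. Under the Inclusion Criteria, cases are histologically confirmed and controls have bilateral plaques or bilateral thickening. Accuracy in such a sample need not hold in exposed people generally or before symptoms. The documents also support no particular prevalence, so a range that stops at 1% could still overstate PPV.

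Three stronger readings are tempting and are not supported:

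- **That Aim 2 as a whole is invalid.** Sensitivity and specificity do not depend mathematically on the 35:65 split, and comparing VOC with Mesomark at one common mix is fair.
- **That the incidence of about 2 per 100,000 supplies the missing prevalence.** It is a background incidence and is not linked to the analysis.
- **That the discontinuation rule in Section F is shown to be faulty on this ground.** That rule governs whether the study goes on from Phase 1, which is recruited 100:100, and it needs a separate argument.

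**Conclusion.** The concern holds in this limited form. Section F makes PPV and NPV part of predictive capability on a sample whose case share is fixed at 35% by recruitment, and the supplied text names no target prevalence or adjustment. For any imperfect test, the raw values describe that mix and cannot be read as predictive values for asbestos-exposed people.

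The size depends on assumed accuracy and prevalence. For the three accuracy pairs in Step 2, moving from the study mix to a 1% prevalence takes PPV from 65–98% down to 3.4–49%, while NPV moves in the favourable direction. That the values change with case share is certain. How far they change for the real target population is unknown, because the documents give no prevalence for it. The point should be fixed, but it does not threaten the usability of the data.

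**What to change.** In Section F, for Aim 2:

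1. Make sensitivity and specificity, each with a 95% CI, the main measures.
2. Label any in-sample PPV or NPV as specific to the 35% case mix.
3. Where PPV and NPV are given for asbestos-exposed people, derive them by Bayes' rule from Phase 2 sensitivity and specificity, with 95% CIs, over one prespecified prevalence range. Use the same range for VOC, Mesomark and their combination. Since the analysis is split between two companies, fix the range before either begins.
4. Have the sponsor justify the range from a source or label it an assumption. It should extend below 1% unless a source supports a higher floor.
5. State that the intervals cover sampling error only. State also that the projections assume accuracy in histologically confirmed cases, and in controls with bilateral plaques or bilateral thickening, carries over to the target population.

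If the document named in Section D already contains such text, carrying it into Section F is enough.

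The cost is a few sentences and no extra data. The downside is that the projections rest on an assumed prevalence and on transportability. If target prevalence is below 35%, the reported PPV will be less favourable than the raw figure and the reported NPV more favourable.
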